Statistical Design and Power	For this pilot trial, enrolling 50 patients (25 per arm) would lead to approximately 81% power to detect a difference in mean platelet levels at the time of transfusion, assuming an autocorrelation between platelet levels at the time of transfusion of 0.3, a difference between the pre- transfusion platelet counts of 30, and a standard deviation of the pre- transfusion platelet count of 40.
Subject Participation Duration	Subjects will be enrolled over a 24-month period (quarter 3 to 10 of the study). Each patient will be followed daily until 24 hours past the treatment strategy's expiration (i.e., until at most day 22 after randomization). Mortality will be measured at day 28 (+/- 4 day window) and day 90 (+/- 10 day window).

3. Study Teams

A. Co-Principal Investigators

[name], MS Division of Pediatric Critical Care Medicine Weill Cornell Medicine [name] [contact]

B. Executive Committee

[name] Nationwide Children's Hospital Columbus, OH [contact]

[name] Sainte Justine Hospital Montreal, QC, Canada [contact]

[name] John Radcliffe Hospital Oxford, UK [contact]

[name], MSCE Nemours Children's Hospital Wilmington, DE [contact] [name], PhD Section of Pediatric Critical Care Medicine Yale School of Medicine [name] [contact]

[name] University of Pittsburgh Pittsburgh, PA [contact]

[name] Sainte Justine Hospital Montreal, QC, Canada [contact]

[name] Norfolk and Norwich University Hospital Norwich, UK [contact]

C. Statisticians and Data Coordinating Center

[name] Statistician University of Utah Salt Lake City, UT [contact]

[name] Statistician University of Utah Salt Lake City, UT [contact] [name] Coordinator Trials Innovation Network University of Utah Salt Lake City, UT [contact]

D. Participating Institutions and Principal Investigators

[name], DO Children's Hospital of Richmond Richmond, VA [contact]

[name] Komansky Children's Hospital of NY Presbyterian New York, NY [contact]

[name] Golisano Children's Hospital Rochester, NY [contact]

[name] Children's Hospital of Wisconsin Milwaukee, WI [contact]

[name] Duke University School of Medicine Durham, NC [contact] [name] Norton Children's Hospital Louisville, KY [contact]

[name] Morgan Stanley Children's Hospital of NY Presbyterian New York, NY [contact]

[name], MS University of Iowa Health Care Iowa City, IA [contact]

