For the *pilot study*, the analysis of the primary outcome measure will be assessing the pretransfusion platelet count to describe the separation between the two platelet transfusion strategies, while accounting for intra-subject correlation. For each arm, we will estimate the mean pre-transfusion platelet count throughout the ECMO runs. This primary outcome will be measured for each transfusion and represent the latest available collected platelet count that is before the transfusion began. In the event that there was no preceding platelet count since a previous transfusion, the outcome for that transfusion will be regarded as missing. Participants who do not have a non-missing value for this outcome (e.g., they had no transfusions) will not be included in the analysis of the primary outcome. Because we anticipate intra-subject correlation when there are multiple transfusions for a patient, we will fit a linear model to pre-transfusion platelet counts with a fixed effect for assigned treatment (higher threshold vs. lower threshold). We will account for repeated measures by considering three within-subject covariance structures with constant variances: compound symmetry; the continuous analog of an autoregressive order 1 process, also known as CAR(1); and a hybrid of compound symmetry and CAR(1) achieved by including random subject effects and CAR(1) correlations in the within-subject errors. We will use restricted maximum likelihood (REML) for model estimation and use the model with the lowest Akaike Information Criterion (AIC) to select the best covariance structure. Once the covariance structure

is determined, the Kenward-Roger calculation for denominator degrees of freedom (df) will be applied in the F-test (equivalently, for the df in the t-test) of the treatment strategy's model coefficient. The test of the null hypothesis that the mean pre-transfusion platelet count is the same for each treatment arm vs the alternative that the higher threshold has a higher mean will be considered statistically significant if and only if the one-sided p-value is less than 0.025. In addition, a two-sided 95% confidence interval for the difference in means will be reported along with estimates of each treatment's mean and the difference in means, with all inferences coming from the repeated measures model described above.

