The sixth feasibility criterion's outcome is defined for a combination of platelet-count level and platelet-transfusion-level observations. Adherence is indicated by having an appropriately dosed platelet transfusion within 12 hours after a below-threshold platelet count, and by not having any platelet transfusion when there is no below-threshold platelet count. In general, there is one adherence/non-adherence determination per platelet count (although some are excluded, and some additional determinations can apply when a transfusion occurs without any platelet count in the previous 12 hours).

	,	Platelet Transfusion			
		Yes	Νο	Excluded transfusion(s) was the only transfusion within 12 hours after platelet count ^a	
Platelet count	Yes	Adherence ^{b,c}	Non-adherence ^c	Adherence	
below threshold	No	Non-adherence ^b	Adherence	ignored	
	Excluded platelet count ^d	Non-adherence ^b	ignored	Ignored	

^a Platelet transfusions are excluded if any of the following apply: transfusion start time before randomization or after the time the strategy was permanently terminated; transfusion start time during a period of temporary suspension

^b The transfusion is considered non-adherent if an included (i.e., not excluded) platelet transfusion did not have a below-threshold platelet count as the most recent platelet count, or if there was an absence of a platelet count within 12 hours prior to the transfusion start time, or the most-recent platelet count was at or above the threshold.

^c The platelet count is considered non-adherent if an included (i.e., not excluded) platelet count was below the threshold and there was no platelet transfusion (not known to be at an inappropriate dose) within 12 hours after the platelet count.

^d Platelet counts are excluded if any of the following apply: was more than 12 hours prerandomization; was after the time the strategy was permanently terminated; was prior to randomization, and before randomization had a transfusion and/or another pre-randomization platelet count; was a below-threshold count but within 12 hours after the blood sample was collected, and prior to a subsequent platelet transfusion, there was either a platelet count at or above the threshold or the transfusion strategy was permanently terminated; was a platelet count at or above the threshold but within 12 hours and prior to a blood transfusion, there was either a below-threshold platelet count or the transfusion strategy was permanently terminated.

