The first objective is based on the primary outcome of platelet counts before transfusions. Because we anticipate intra-subject correlation when there are multiple transfusions for a participant, we will fit a linear model to pre-transfusion platelet counts with a fixed effect for assigned treatment (Higher threshold, with tmt=1, vs Lower threshold, with tmt=0), such that the outcome's expected value is represented by $\beta_0 + \beta_{tmt}$ for the higher threshold and β_0 for the lower threshold. We will account for repeated measures by considering three covariance structures: compound symmetry (CS), continuous analog of autoregressive order 1, also known as CAR(1), and a hybrid of CS and CAR(1) achieved by including random subject effects and CAR(1) correlations in the within-subject errors. We will use restricted maximum likelihood (REML) for model estimation and use the model with the lowest Akaike Information Criterion (AIC) to select the best covariance structure. Once the covariance structure is determined, the Kenward-Roger calculation for denominator degrees of freedom (df) will be applied in the F-test (equivalently, for the df in the t-test) of the treatment strategy's model coefficient. The one-sided p-value of the null hypothesis $\beta_{tmt} = 0$ vs $\beta_{tmt} > 0$ will be considered statistically significant if and only if this p-value < 0.025. In addition, a two-sided 95% confidence interval for β_{tmt} will be reported. Likewise, estimated means for the lower threshold and the higher threshold arms will be reported as $\hat{\beta}_0$ and $\hat{\beta}_0 + \hat{\beta}_{tmt}$ respectively.

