8 SAMPLE SIZE DETERMINATION

The trial has two primary types of formal statistical inferences: testing for separation in the primary outcome of Aim 1—pre-transfusion platelet counts—between transfusions with non-missing pre-transfusion platelet counts from ITT participants in the two study arms at the end of the study, and ongoing testing for differences in the proportions of SAFETY participants with the primary safety outcome between arms for an interim safety stopping rule and/or end-of-study evaluation. While the study is powered for the Aim 1 primary outcome, it is not intended to be powered for a difference in the primary safety outcome in the ECSTATIC trial.

Salient assumptions to permit power estimation include the number of observed transfusion days per subject, the within-subject dependence structure, the within-treatment variability, and the difference in means between treatments. Previous data, albeit not with an enforced low platelet threshold transfusion strategy, were used to inform the first three assumptions. It was assumed the distribution of the number of transfusion days per subject will mimic historical data (e.g., approximately 10%-20% will have no transfusions). It was assumed a compound symmetry covariance structure will adequately account for within-subject dependence; such a structure is induced by a mixed effects model with subject-specific random intercepts. Fitting a model with such a covariance structure to historical data [4] yielded an estimated autocorrelation slightly above 0.2; to be conservative the power estimation assumed $\rho = 0.3$. The assumed within-treatment standard deviation, $40 \times 10^9/L$, resembles historical data but is anticipated to be a conservative estimate for the trial.

Although the difference in platelet strategy thresholds is $40 \times 10^9/L$ (i.e., $90 \times 10^9/L$ vs $50 \times 10^9/L$), this full effect will not be realized for the mean difference because the strategies depend on platelet counts which are not continuously observed, and as such, by the time of measurement a patient may have a platelet count considerably below the threshold. Patients with a platelet count under $50 \times 10^9/L$ would be transfused under either strategy. Therefore, a more realistic separation for the difference in means between strategies is $30 \times 10^9/L$.

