Assuming pre-transfusion platelet levels will be approximately normally distributed with a difference in means of $30 \times 10^9/L$, then with 50 patients (25 per arm) enrolled (and thus an estimated effective sample size of 30 statistically independent observations per arm when

accounting for patients with no transfusions, patients with multiple transfusions, and the assumed within-subject dependence in the outcome) there would be approximately 81% power to detect a difference in mean platelet levels at the time of transfusion. Power may be higher due to conservative assumptions.

9 References

References

- [2] [name] ME, Tucci M, Lacroix J, Spinella PC, Haque KD, Stock A, et al. Bleeding Assessment Scale in Critically Ill Children (BASIC): Physician-Driven Diagnostic Criteria for Bleeding Severity. Crit Care Med, 2019 Dec; 47(12): 1766–72.

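### The Aim 1 model is valid and its 81% power reproduces, but it omits the captured pre-randomization platelet count and so probably gives up some precision

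*Combined protocol and SAP*

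**What the plan says.** SAP 7.2.1 and protocol 10.C describe the same primary model: "we will fit a linear model to pre-transfusion platelet counts with a fixed effect for assigned treatment". Repeated counts in a child are handled by a covariance structure chosen by AIC, with REML estimation and Kenward-Roger degrees of freedom. The result is "considered statistically significant if and only if the one-sided p-value is less than 0.025". The same fit supplies the 95% confidence interval and the estimate that SE1 compares with 30 ×10⁹/L (SAP 2.2.2 and 7.3.1).

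This is the only analysis that the trial is sized for. SAP 8 says "While the study is powered for the Aim 1 primary outcome" and that the safety outcome is not powered. On the planning assumptions, "there would be approximately 81% power to detect a difference in mean platelet levels at the time of transfusion".

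A pre-randomization count is in the data. Appendix F, note d, drops a count from the adherence score if it was taken more than 12 hours before randomization, or if it "was prior to randomization, and before randomization had a transfusion and/or another pre-randomization platelet count". The latest eligible count before randomization therefore remains and is scored. Protocol 11.A also lists data collection at cannulation and at randomization, without naming the platelet count.

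Neither document adjusts any model for this count. SAP 5.4 and 7.6 mention ECMO type, age and site for exploratory, subgroup or supplementary work. A reason for leaving a covariate out of the primary model is given for site only (risk of non-convergence).

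**The concern.** An earlier value of the outcome variable is usually the first candidate for covariate adjustment. The plan's sample size calculation assumes that counts within a child are correlated, so part of the outcome variance is a persistent child-level component. A baseline count can explain some of that part at little cost.

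Three results depend on this one fit: the Aim 1 test, its confidence interval and SE1. SE1 compares a point estimate with a fixed cut-off that equals the planning difference, so modest chance differences in starting count could tip it either way. Only children with at least one usable pre-transfusion count contribute, which leaves about 20 to 22 per arm.

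**Working it through.** **Inputs**
- Difference 30 and SD 40 ×10⁹/L: protocol Abstract, "a difference between the pre- transfusion platelet counts of 30, and a standard deviation of the pre- transfusion platelet count of 40".
- Effective sample of 30 independent observations per arm from 25 enrolled: SAP 8.
- 10-20% with no transfusion, so 25 × 0.8 = 20 to 25 × 0.9 = 22.5 contributing children per arm: SAP 8.
- Within-child correlation 0.3. The historical estimate was slightly above 0.2, and "to be conservative the power estimation assumed" 0.3: SAP 8.
- One-sided alpha 0.025: SAP 7.2.1, protocol 10.C.
- Correlation r between the baseline count and a single pre-transfusion count: **not in the documents**. It is an assumption, shown as a range.

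**Step 1: the plan's own figure.** SE = 40 × √(2/30) = 10.33. Noncentral t with 58 df gives 81.5%, and with 40 df 80.9%. The normal approximation gives 82.8%. The stated 81% reproduces.

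**Step 2: adjusting the effective sample.** The residual SD becomes 40 × √(1 − r²), with t on 57 df. Power is 81.9% at r = 0.1, 83.0% at 0.2 and 84.9% at 0.3.

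**Step 3: removing between-child variance only.** With n children per arm, let e = 30/n. The implied number of transfusions per child is m = 0.7e / (1 − 0.3e):
- n = 20: e = 1.50, m = 1.05/0.55 = 1.91
- n = 22.5: e = 1.33, m = 0.933/0.60 = 1.56

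The variance of a child mean, in units of 40², is 0.3 + 0.7/m before adjustment (0.667 and 0.750). After adjustment it is 0.3 − r² + 0.7/m. The within-child correlation stays at 0.3 throughout.

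| r | variance ratio | SE | power (t, 57 df) |
|---|---|---|---|
| 0 | 1 | 10.33 | 81.5% |
| 0.1 | 0.985-0.987 | 10.25-10.26 | 82.0% |
| 0.2 | 0.940-0.947 | 10.01-10.05 | 83.5-83.8% |
| 0.3 | 0.865-0.880 | 9.61-9.69 | 86.1-86.7% |

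For example, at r = 0.3 and n = 20, (0.667 − 0.09)/0.667 = 0.865 and 10.33 × √0.865 = 9.61.

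Steps 2 and 3 together give about 83-87% for r = 0.2 to 0.3. A child-level weighted-regression simulation (21 per arm, 1-3 transfusions each) gave a smaller gain at r = 0.3, from 79% to 82%.

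**Step 4: SE1.** Assume a baseline SD of 40 and 21.25 children per arm (15% untransfused). The difference between arms in mean baseline then has SD 40 × √(2/21.25) = 12.3. A one-SD imbalance moves the unadjusted separation by r × 12.3, which is about 2.5 at r = 0.2 and 3.7 at r = 0.3. This shift is already part of the SE of 10.33, not an extra error.

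**Step 5: does the threshold weaken r?** Simulations of threshold-triggered transfusion depend wholly on assumed count trajectories. One gave a baseline-to-mean correlation of 0.14 under the lower threshold and 0.40 under the higher. Others cut the standard error by 0-2% under one set of assumptions and by 11-30% under another. They show only that the gain is uncertain.

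**The case against.** The strongest reply is that nothing is wrong with the plan. A treatment-only repeated-measures model is valid under randomization, its confidence interval already carries chance imbalance, and SAP 8 calls the SD and correlation conservative. All of that stands. A reader might infer that the trial is underpowered or its estimate biased by the omission; the documents support neither.

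The benefit also rests on a missing number. The 0.3 was set above the historical value to be cautious about power, so it is not evidence for a large gain, and the historical data came without an enforced low threshold. A pre-transfusion count is normally one that has just fallen below 50 or 90, which may loosen its link to the starting count. A reader might take r = 0.4 or 0.5, where Step 3 gives about 90% to 95%. Those values exceed the plan's within-child correlation, and no passage supports them.

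The remedy has complications too. The outcome is the latest count before a transfusion, with no requirement that it follow randomization. A baseline of 50-89 calls for transfusion in the higher arm but not in the lower, so baseline and first outcome can coincide, more often in the higher arm. Nor does a baseline covariate reliably repair selection into the set of transfused children. These points stand and shape the fix; they do not remove the case for it.

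Last, SAP 5.4 notes how little information there is even for main effects. It says so of exploratory models, and it does not address a single continuous covariate in the primary one.

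**Conclusion.** The point holds as a low-priority efficiency improvement. The only powered model omits a captured prognostic count and gives no reason specific to it. At r = 0.2 to 0.3, power would rise from about 81% to about 83-87% and the SE would fall from 10.33 to about 9.6-10.1. At r = 0.1 or below the gain is negligible. The figures rest on the plan's difference, SD, effective sample and within-child correlation, and on an assumed r.

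One might also infer that adjustment would change the trial's go/no-go decision. The documents do not show that: SE1 is one of ten criteria, of which five must be met. It is still enough reason to settle the deciding estimate beforehand. Because only transfused children contribute, adjustment can move the estimate as well as its precision; in one illustrative high-compliance simulation the separation went from 25.7 to 23.5.

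That the count is captured is inferred from Appendix F of protocol version 1.4. The SAP was written to protocol version 1.3.1 and does not name the count among its baseline variables.

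**What to change.** Amend SAP 7.2.1 and protocol 10.C as follows:
- Add the last pre-randomization platelet count as a continuous fixed covariate for the Aim 1 test and 95% confidence interval. Define it exactly: the look-back window, and whether a count followed by a transfusion before randomization qualifies.
- State a rule for missing baselines that does not depend on arm.
- Keep the treatment-only model as a sensitivity analysis.
- Add a sensitivity analysis that excludes outcome records in which the baseline count is itself the pre-transfusion count.
- Name the model whose estimate decides SE1.

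The statisticians are not blinded (protocol 8.F, SAP 3.3), so the amendment should be dated before any comparison of platelet counts by arm.

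The cost is a few sentences and one degree of freedom, with no new visits or patients. The downsides are the arm-dependent overlap between covariate and first outcome value, and a possible small shift in the estimated separation. The two sensitivity analyses would show both.

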7.2.2 Additional Analyses

We will measure the effect of the days on ECMO, by providing summaries of the daily platelet counts for each specific ECMO day with ≥ 5 patients still on ECMO, independent of receiving a platelet transfusion. This will allow evaluating trends over time and a possible attenuation of the separation over time. The raw summaries for such days will be reported. As another analysis we will fit a linear model with a main linear effect for study day, a main effect for assigned treatment, a treatment by time interaction effect, and the best-fitting covariance structure, per AIC, among compound symmetry, CAR(1), the CS/CAR(1) hybrid, and subject-specific random intercepts and random time slopes. A two-df Wald test with Kenward-Roger denominator df and REML estimation will be conducted for the null

hypothesis that both the treatment main effect and the treatment by time interaction effect are 0. If this test is rejected at $\alpha = 0.05$, the interaction effect will be separately tested with a two-sided alternative at $\alpha = 0.05$. Then, if the 2-df test was significant but the 1-df test of the interaction effect was not significant, the main effect of treatment will be tested against a two-sided alternative at $\alpha = 0.05$.

Furthermore, we will also estimate the difference in the median platelet transfusion dose (in mL/kg/run) between the lower and higher platelet threshold strategy arms, and the median daily platelet transfusion dose (in mL/kg/day, i.e., $24 \times mL/kg/hr$) to account for different durations of treatment strategies. These outcomes will use two-sided nonparametric percentile bootstrap 95% confidence intervals, based on a minimum of 10,000 bootstrap replicates, for the difference in medians because by construction for each of these outcomes, there is only one outcome per person. As such, repeated measures modeling is not warranted.

